7.8. Randomisation

A web-based permuted block randomisation procedure (sealedenvelope.com) will be used to allocate participants into one of the study arms: 1) usual care alone; 2) aerobic exercise training plus usual care. Participants will be stratified using the National Institutes of Health Stroke Scale (NIHSS): mild to moderate (0-15) and moderate to severe (>15) measured after reperfusion therapy or at a similar timepoint if not eligible for reperfusion therapy. Block

sizes of either 4 or 6 will be randomly chosen and block size will be masked from research team members involved in patient-facing research activities. An independent research team member will be responsible for the block randomisation procedure. They will be notified via email with participant ID numbers and a corresponding NIHSS score using a remote web-based system. The independent research team member will publish the group allocation which will be remotely accessible only to authorised research team members.

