7.3. Sample size

A minimum of 24 participants (12 per arm) will be recruited. 12 has been recommended as a minimum number of participants per arm to be recruited for a clinical trial where there is no prior information to guide sample size (60). This figure is suggested to represent the lower threshold required to estimate the standard deviation of measures with adequate precision (60). Adjusting for a predicted 20% attrition rate, the target sample size is 30.

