7.6. Patient screening

The Study Doctor will review patients' clinical data to determine eligibility in accordance with the inclusion and exclusion criteria. Patients will be screened for absolute and relative contraindications to aerobic exercise prior to participation (Table 1, section 8.1). Absolute contraindications will preclude individuals from undertaking aerobic exercise. The Study Doctor will use clinical judgment to determine if individuals with relative contraindications to aerobic exercise can participate. Established exercise termination criteria (Table 2, section 8.2) will be used to minimise risk of harm during aerobic exercise.

The following routine medical examinations and clinical information will be used to determine eligibility and stratification:

- Time and date of stroke onset.
- Stroke treatments initiated.
- Stroke severity.
- Medication use.
- Electrocardiography results.
- Blood test results.
- Neuroimaging results.
- Carotid ultrasound imaging results.
- Comorbidities.

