7.9. Blinding

It is not possible to blind participants or on-site research team members to group allocation. Statistical analyses will be conducted by an independent research team member who is blinded to group allocation.

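### The protocol prints the block sizes in the sentence that says they are masked from patient-facing staff, so about 5-6% of allocations become certain to a recruiter who keeps a tally (minor)

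*Protocol*

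**What the plan says.** Protocol section 7.8 (Randomisation) describes the method: "A web-based permuted block randomisation procedure (sealedenvelope.com) will be used to allocate participants into one of the study arms". The allocation is stratified by stroke severity in two strata, NIHSS 0-15 and above 15. On blocking, the section says that "sizes of either 4 or 6 will be randomly chosen and block size will be masked from research team members" who deal with patients. An independent team member runs the procedure, receives the participant ID and NIHSS score remotely, and releases the allocation to authorised staff.

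Four other places set the conditions in which this operates:

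- Section 6.1 makes the trial single-centre.
- Section 7.2 has the Study Doctor identify patients and approach them with an Investigator.
- Section 7.6 leaves part of the entry decision to judgement: "The Study Doctor will use clinical judgment to determine if individuals with relative contraindications to aerobic exercise can participate".
- Section 7.9 states: "It is not possible to blind participants or on-site research team members to group allocation".

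Section 12.6 requires the Principal Investigator, the Study Doctor and the Co-Investigators each to adhere to the whole protocol, so all of them work from the text that contains section 7.8.

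**The concern.** The sentence in section 7.8 partly defeats itself. It withholds block size from the people who recruit and treat, and it tells those same people that the size is 4 or 6. At one site with an unblinded team, past allocations are known. Anyone who keeps count can combine them with the two printed sizes and will sometimes know the next arm for sure.

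Foreknowledge matters because there is room to act on it. The Study Doctor judges relative contraindications, and section 7.2 allows up to 48 hours between first discussion and decision, which gives some freedom over timing. If patients were approached or timed according to the expected arm, baseline comparability would suffer. So could the exclusion and consent rates, which are feasibility outcomes in Table 6, and the between-group effect signal that Aim 4 in section 5 wants to estimate. The concern is about opportunity. Nothing in the protocol shows that steering would occur.

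**Working it through.** **Inputs**

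- Two arms, 1:1. Section 7.3: "A minimum of 24 participants (12 per arm) will be recruited".
- Total number. Section 7.3: "Adjusting for a predicted 20% attrition rate, the target sample size is 30".
- Block sizes 4 or 6, chosen at random (section 7.8). The two are assumed equally likely.
- Two NIHSS strata (section 7.8). The split of participants between them is not stated, so it is varied.
- Past allocations known to recruiters (section 7.9).

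**Step 1: reproduce the plan's own figure.** 24 / (1 - 0.20) = 30, which matches. The protocol states no guess probability.

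**Step 2: guess rate in complete blocks, without using block size.** The guesser always names the arm that is behind and tosses a coin when the arms are level. In a complete block of size 2m the expected number of correct guesses is m + 2^(2m-1)/C(2m,m) - 1/2.

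- Size 4: 2 + 8/6 - 0.5 = 2.833, and 2.833/4 = 70.8%.
- Size 6: 3 + 32/20 - 0.5 = 4.1, and 4.1/6 = 68.3%.
- Equal mix in the long run: (2.833 + 4.1)/(4 + 6) = 6.933/10 = 69.3%.

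**Step 3: the same strategy with 30 participants and blocks cut off at the end of each stratum** (60,000 simulated sequences).

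| Split between strata | Correct guesses |
|---|---|
| 30 / 0 | 68.8% |
| 27 / 3 | 67.4% |
| 25 / 5 | 67.6% |
| 20 / 10 | 68.3% |
| 15 / 15 | 67.6% |

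For example, the 27/3 row is (27 x 0.6836 + 3 x 0.589)/30 = 0.674. If the recruiter ignores strata and keeps one pooled tally, the rate is 63-64%.

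**Step 4: does knowing the sizes raise the guess rate?** The best possible guesser, who knows the sizes are 4 or 6 but not where blocks begin or end, was followed by Bayesian updating (20,000 sequences). The result is 67.6% for a stratum of 15 and 68.8% for 30. These are the values for the strategy that uses no sizes, so there is no detectable gain.

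**Step 5: what does knowing the sizes give?** It gives certainty at some points. At the start of a stratum, for instance, three identical allocations in a row cannot come from a block of 4. The block must be a 6, and the next three allocations are known. Over whole sequences the share of certain allocations is:

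- 5.7% for one stratum of 30, and 0.057 x 30 = 1.7 allocations;
- 5.9% for a stratum of 15;
- 5.1% for a 27/3 split.

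For comparison, a single fixed and known size would make about 31% of allocations certain with blocks of 4 and about 25% with blocks of 6.

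**Step 6: effect of hiding the sizes.** Certain predictions need the sizes, so the 5-6% disappears. The guess in steps 2 and 3 does not need them, so the 67-69% stays.

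**The case against.** The strongest defence is that section 7.8 masks which size each block has, and that this remains masked because sizes are drawn at random and the sequence of sizes is not printed. On that reading the masking largely works: certain allocations are held to 5-6% where fixed sizes would give 25-31%. This stands, and it is the main reason the point is small. It does not remove the point, because the set of sizes is still disclosed to the people from whom block size is meant to be withheld, and that disclosure is what creates the certain allocations.

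The other safeguards also count. The list is run by an independent person, allocation is requested remotely by ID and NIHSS score, and random block sizes with an independent allocator are a defensible design. These measures protect the list itself. They do not prevent inference from allocations already seen.

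The consequences are limited as well. The trial asks about feasibility, and none of the success criteria in section 6.3 is a comparison between arms. The consent rate is an outcome in Table 6 but not one of those criteria. The higher guess rate also requires a running tally by stratum.

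A reader might go further and infer that printing the sizes is what lets recruiters guess two in three allocations, so that masking has failed. The documents do not support this. Steps 3 and 4 give the same rate with and without the sizes. The rate follows from small 1:1 blocks with an unblinded team and says nothing about whether masking works.

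**Conclusion.** The point holds in a limited form and is minor: an easy improvement, with nothing here that undermines the trial. Section 7.8 discloses the set of block sizes it says is masked. The cost of that disclosure is that about 5-6% of allocations, about 1.7 of 30, are certain to a recruiter who has read the section.

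A separate feature of the design is that 67-69% of allocations can be guessed with a tally per stratum, or 63-64% with a pooled tally, whether or not the sizes are known.

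These figures assume that the two sizes are equally likely, that recruiters know all earlier allocations, and that they keep count. They measure the scope for selection. They are not evidence that selection happens, and no size of bias in any outcome can be derived from the protocol.

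**What to change.** In section 7.8, delete the two numbers. State only that block sizes vary at random and are held by the independent team member in a file that patient-facing staff cannot open. Because staff may already have read the present text, that member should also reset the sizes, undisclosed, before the first patient. The cost is one sentence of protocol wording and one newly generated list.

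The amendment should be plain about what it achieves. It makes the masking statement true and removes the certain allocations, but the two-in-three guess rate remains. Larger random blocks would lower that rate only modestly: in a single stratum of 30, sizes 6, 8 or 10 give 65.6%, and sizes 8 or 12 give 64.0%.

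Replacing blocks with a procedure that only caps the imbalance (a big-stick list with limit 3) is not recommended here. It lowers average guessing to about 58% in a single list of 30. However, 13-15% of allocations would be forced for anyone who learned the limit, and with separate NIHSS strata the overall imbalance can reach 4 to 6. That is a real drawback when section 7.3 needs at least 12 per arm out of 30 recruited.

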7.9. Blinding

It is not possible to blind participants or on-site research team members to group allocation. Statistical analyses will be conducted by an independent research team member who is blinded to group allocation.

7.10. Payment

Reasonable travel expenses will be provided for follow-up appointments located at the AWRC or BHRU. This will cost approximately £600 (30 x £20) and will be funded by a PhD research budget.

7.11. Physical accessibility

Participants will be invited to attend routine follow-up clinics with [name] at 2 weeks and 3 months post-stroke. These will take place at the RHH, AWRC or BHRU. The location will depend upon where [name] clinics are scheduled. The RHH, AWRC and BHRU are accessible for people with physical impairments; each building has ramps and elevators. The AWRC and BHRU have car parking facilities which are free of charge. Parking spaces will be reserved for participants and research team members attending the AWRC and BHRU. The RHH has a large pay-and-display car park. Each building has emergency evacuation strategies for people with physical disabilities.

8. Safety

8.1. Contraindications to aerobic exercise

Patients' medical notes will be reviewed by the Study Doctor to identify absolute and relative contraindications to aerobic exercise. Absolute contraindications are conditions or situations in which an intervention/procedure should not be performed due to a disproportionately high

risk of harm. Patients with absolute contraindications will be excluded from the study. Relative contraindications are conditions or situations in which an intervention/procedure should be used with caution if the benefits outweigh the risks (determined by the Study Doctor).

Table 1. Contraindications to aerobic exercise.

Absolute contraindications	Relative contraindications
Acute myocardial infarction (within 3–5 days)	Left main coronary stenosis or its equivalent
Resting ST segment displacement (>2 mm)	Moderate stenotic valvular heart disease
Significant aortic stenosis (aortic valve area <1.0 cm ²)	Tachyarrhythmia or bradyarrhythmia
Uncontrolled sinus tachycardia (HR >120 bpm)	High-degree atrioventricular block
Third degree (complete) atrioventricular block without pacemaker	Hypertrophic cardiomyopathy
Active endocarditis	Significant pulmonary hypertension
Unstable angina	Electrolyte abnormalities
Uncontrolled hypertension: resting systolic blood pressure (SBP) >180mmHg, or resting diastolic blood pressure (DBP) >110mmHg	Use of insulin or insulin secretagogues
Orthostatic blood pressure drop of >20 mmHg with symptoms	Orthopaedic impairment
Syncope	Advanced or complicated pregnancy
Uncontrolled arrhythmias causing symptoms or haemodynamic compromise	
Acute myocarditis or pericarditis	
Uncontrolled heart failure	
Severe grade 3 rejection (cardiac transplantation recipients)	
Acute pulmonary embolus or pulmonary infarction	
Thrombosis of lower extremities	
Suspected dissecting aneurysm	
Uncontrolled asthma	
Pulmonary oedema	
Room air desaturation at rest <85%	
Respiratory failure	
Acute noncardiopulmonary disorder that may affect exercise performance or be aggravated by exercise (i.e. infection, renal failure, thyrotoxicosis)	
Uncontrolled diabetes mellitus	
Other metabolic conditions, e.g. acute thyroiditis, hypokalaemia, hyperkalaemia or hypovolaemia (until adequately treated)	
Acute systemic illness or fever	
Medically unstable	
Cognitive impairment leading to inability to cooperate	

Note. Table adapted from (43,59,60).

8.2. Aerobic exercise termination criteria

Table 2. Aerobic exercise termination criteria.

Termination criteria
†CBF velocity 30% below baseline
Chest pain suggestive of ischaemia
Fall in systolic blood pressure >20 mmHg from the highest value during exercise
>225 mmHg systolic blood pressure
>130 mmHg diastolic blood pressure
Hypotension (<100 mmHg systolic)
Severe desaturation: SpO ₂ ≤ 80% when accompanied by symptoms and signs of severe hypoxaemia
Sudden pallor
Loss of coordination
Mental confusion
Dizziness or faintness
Signs of respiratory failure

Note. Table adapted from (45,61,62); † = Study Doctor's clinical judgement.

8.3. Safety of aerobic exercise

Low- to moderate-intensity aerobic exercise is considered to be safe for medically stable acute ischaemic stroke patients without contraindications (44,63). The only study which has conducted a moderate-intensity aerobic exercise training intervention (five days of twice-daily, 30-min bouts of moderate-intensity walking exercise) reported no SAEs but occasional dizziness (8.5%; 19/224 sessions) and exhaustion (44). Exhaustion is not classed as an AE but is an important outcome when considering exercise tolerability; 24 out of 224 (10.7%) exercise sessions ended early as a result of exhaustion (9/20 participants). In addition, Kramer et al., (64) investigated the energy cost of two different 6-minute fitness assessments in acute stroke patients (median 4 days post-stroke; mild to moderate stroke; n=21). Ambulatory participants (n=14) performed a 6-minute walk test, whereas non-ambulatory participants (n=7) completed a 6-minute sit-to-stand test. The median rating of perceived exertion (RPE) reported at the end of each test was 12/20 and 13/20 for the walk and sit-to-stand tests, respectively (both moderate intensity). No SAEs or AEs were reported, and only one participant was unable to complete the walk test due to fatigue. Furthermore, Johnson et al., (65) demonstrated the safety of a graded exercise test in acute

and subacute stroke patients (n=28, days post-stroke: median = 9; range = 5-11), although the authors did not specify the proportion of participants that were in the acute (1-7 days post-stroke) or early subacute phase of stroke (7-30 days post-stroke). One of the exercise test termination criteria was reaching 85% of age-predicted maximum heart rate (HRmax), which is classed as vigorous exercise intensity (45). Over half of the participants exceeded this upper heart rate threshold and no SAEs or AEs were observed. Lastly, in our preliminary work (ESCAPE trial; STH20750), 4 acute stroke patients successfully completed a single 30-minute moderate-intensity exercise session (13/20 RPE) and there were no AEs or SAEs. Importantly, none of the aforementioned studies reported follow-up safety outcomes. **We can confirm that there have been no SAEs or AEs related to aerobic exercise in the 3 months following our investigation.** In summary, there have been approximately 276 reported bouts of aerobic exercise conducted in the acute phase of stroke, ranging from 6 to 30 minutes in duration and from moderate to vigorous intensity. No SAEs have been reported, whereas the AE rate ranged from 0-14.7% (mean 12%). The higher frequency of AEs appears to be related to high exercise volume and the mode of exercise training (e.g. treadmill exercise twice per day for 5 days).

In our proposed aerobic exercise training intervention, participants will exercise at a moderate intensity (40-59% HRR; 12-13/20 RPE). Moderate-intensity aerobic exercise elicits a transient increase in cerebral perfusion and neurotrophin concentration (39,59) which may contribute to improved recovery after stroke (24–26). Exercise duration will gradually increase from 10 minutes in the first session (day 1) to 30 minutes in the fifth session (day 5) (5-minute increment per day). Heart rate (HR) will be monitored continuously during exercise to ensure that moderate intensity is not exceeded. Heart rate reserve – the difference between resting HR and HRmax – represents the capacity for the HR to increase under stress. Measurement of HRmax is not appropriate due to the required vigorous exercise intensity. Instead, age-predicted HRmax will be calculated using the Inbar equation which estimates HRmax with greater accuracy than the commonly used formula of 220-age (66).

Inbar equation: $205.8 - (0.685 \times \text{age})$.

To adjust for use of beta-blocker medication, age-predicted HRmax will be reduced by 30 beats (62). The following Karvonen method will be applied to determine the target exercise HR (67). Importantly, this will enable the identification of the upper limit of the moderate exercise intensity domain (60% HRR).

Karvonen method example: target HR = $[(\text{HRmax} - \text{resting HR}) \times 60\%] + \text{resting heart rate}$.

Peripheral oxygen saturation and brachial blood pressure will also be measured throughout exercise and during the recovery period. The recovery phase will be of sufficient duration (~10 minutes; minimum 5 minutes) to allow physiological measures to return to near baseline levels. If any physiological measures fall outside of pre-determined ranges (see Table 2, section 8.2), or symptoms of clinical worsening arise, exercise will be terminated and a medical professional will be notified immediately.

8.4. Risk management

Cardiovascular risk

Participation in aerobic exercise may increase the risk of cardiovascular complications such as cardiac ischaemia, arrhythmia or hypotension. The use of an appropriate warm-up and cool-down will minimise these risks (62). Participants' physiological response to exercise will be closely monitored during and after exercise. Exercise will be stopped if any adverse signs or symptoms occur (see table 2, section 8.2). The research team are experienced in the supervision of exercise and are trained in cardiopulmonary resuscitation.

Musculoskeletal risk

Participation in aerobic exercise may increase the risk of musculoskeletal injury such as a muscle strain. This risk will be minimised by conducting a graduated warm-up (45) and by following the cycle ergometer manufacturer guidelines regarding correct positioning of participants.

Blood glucose regulation risk

Aerobic exercise has insulin sensitising effects, therefore it is important to consider the use of blood glucose-regulating medication. The prevalence of diabetes mellitus in the acute ischaemic stroke population is 28% (95% CI 26-31%) (68). It is unclear what proportion of this population require insulin or insulin secretagogues. Where patients are receiving insulin or insulin secretagogues (relative contraindications), the Study Doctor will decide if the patient may participate in aerobic exercise at that particular time. To minimise the risk of exercise-induced hypoglycaemia, patients receiving insulin or insulin secretagogues will have their capillary blood glucose levels assessed before and after exercise (69). If blood glucose level is below 4mmol/L prior to exercise, the planned exercise session will be

delayed until euglycemia is achieved. Only clinical staff will be responsible for the provision of medication and carbohydrate.

8.4.1. Risk categorisation

Taking into account the absence of reported SAEs and our risk management procedures, we believe that this intervention is low risk. However, there is a lack of reported long-term follow-up outcomes. Due to this uncertainty, we propose that this intervention should be categorised as type B, that is, somewhat higher than the risk of standard medical care.

8.5. Risks and benefits to be communicated to patients (lay summary):

8.5.1. Potential benefits of aerobic exercise training

- Aerobic exercise training may help the brain recover from injury (neuroprotection). However, this has only been shown in animal studies.
- Aerobic exercise training may help the nervous system adapt after injury and improve learning (neuroplasticity). However, this has only been shown in animal studies.
- Aerobic exercise may help to slow down the loss of fitness, muscle size and muscle strength whilst in hospital.
- Aerobic exercise training may improve mood.

8.5.2. Risks of aerobic exercise training

Previous studies have shown that aerobic exercise is safe for people to do in the first week after stroke. So far, 276 aerobic exercise bouts have been completed in the first week after stroke. 237 sessions (86%) involved walking, 32 sessions (12%) involved seated cycling or stepping, and 7 sessions (3%) involved sit-to-stand exercise. From these studies, we estimate that the risk of:

- Cardiovascular, neurological, or musculoskeletal complications is less than 1% (no adverse events have happened so far).
- Lower-limb pain is less than 2% (adverse events only happened in treadmill exercise).

- Getting a blister or superficial wound on the foot is 1.1% (adverse events only happened in treadmill exercise. Cycling places less pressure on the feet than walking).
- Dizziness is less than 7% (adverse events only happened in treadmill exercise which is possibly related to an upright head position. Cycling will be completed in bed with a reclined backrest).

[figure not shown]

Figure 4. Pie charts displaying the risk of adverse events related to aerobic exercise.

9. Investigations

Table 3. Schedule of investigations and outcome measures. Note: orange ticks indicate standard care.

	Study period																		
	Enrolment	Allocation	Post-allocation																
Post-stroke timeline	24-72 h (study starts)				≥48 h; 5-day intervention								+1 day	Follow-up					
	24-72 h (study starts)				≥48 h; 5-day intervention									+2 weeks	+3 months (study ends)				
Study timeline	t_{-1}	t_0		t_1		t_2		t_3		t_4		t_5		t_6		t_7		t_8	
	Group →	C	I	C	I	C	I	C	I	C	I	C	I	C	I	C	I	C	I
Eligibility screen	✓																		
Informed consent			✓	✓															
Age, sex, ethnicity			✓	✓															
Time since stroke (hours)	✓																		
Stroke severity (NIHSS)			✓	✓											✓	✓		✓	✓
Cardiovascular risk profile			✓	✓															
Group allocation			✓	✓															
Thigh muscle morphology (ultrasound)			✓	✓											✓	✓		✓	✓
Thigh accelerometer fitted			✓	✓															
Inpatient physical activity levels (thigh accelerometer)					✓	✓	✓	✓	✓	✓	✓	✓	✓	✓					

	Study period																	
	Enrolment	Allocation	Post-allocation															
Post-stroke timeline	24-72 h (study starts)				≥48 h; 5-day intervention								+1 day	Follow-up				
	+2 weeks			+3 months (study ends)														
Study timeline	t_{-1}	t_0		t_1	t_2		t_3	t_4		t_5	t_6		t_7	t_8				
	Group →	C	I	C	I	C	I	C	I	C	I	C	I	C	I	C	I	
Thigh accelerometer removed														✓	✓			
Physical function (SPPB, 10-m walk, handgrip strength)		✓	✓											✓	✓		✓	✓
Activities of daily living (Barthel Index)		✓	✓											✓	✓	✓	✓	✓
Disability (mRS)		✓	✓											✓	✓		✓	✓
Acute fatigue (RoFS)		✓	✓		✓			✓			✓		✓	✓	✓		✓	✓
Cognitive function (MoCA)		✓	✓														✓	✓
Chronic fatigue (FSS)		✓	✓														✓	✓
Pre-morbid physical activity levels (GPAQ)														✓	✓			
Anxiety and depression (GAD-7, PHQ-9)		✓	✓														✓	✓
Optimism (rLOT)		✓	✓														✓	✓
Health-related quality of life (EQ-5D)		✓	✓														✓	✓
Exercise self-efficacy		✓	✓											✓	✓		✓	✓
Wrist accelerometer fitted														✓	✓			
Post-discharge physical activity (wrist accelerometer returned)														✓	✓			

	Study period																	
	Enrolment	Allocation	Post-allocation															
Post-stroke timeline	24-72 h (study starts)				≥48 h; 5-day intervention								+1 day	Follow-up				
	+2 weeks			+3 months (study ends)										t ₇		t ₈		
Study timeline	t ₋₁	t ₀		t ₁		t ₂		t ₃		t ₄		t ₅		t ₆		t ₇		
	Group →	C	I	C	I	C	I	C	I	C	I	C	I	C	I	C	I	
Post-discharge physical activity (GPAQ)																	✓	✓
Resting cerebral blood flow velocity (transcranial Doppler ultrasound)					✓	✓							✓	✓				
Resting mature brain-derived neurotrophic factor													✓	✓				
Serious/adverse events			✓	✓	✓	✓	✓	✓	✓	✓	✓	✓	✓	✓	✓	✓	✓	✓
Length of stay														✓	✓	✓	✓	
Qualitative interviews														✓	✓		✓	✓
Aerobic exercise-specific investigations:																		
Δ heart rate (telemetry or ECG)						✓		✓		✓		✓		✓				
Δ blood pressure (oscillometry)						✓		✓		✓		✓		✓				
Δ perceived exertion (RPE scale)						✓		✓		✓		✓		✓				
Δ oxygen saturation (pulse oximeter)						✓		✓		✓		✓		✓				
Δ cerebral blood flow velocity (transcranial Doppler ultrasound)						✓							✓					
Δ mature brain-derived neurotrophic factor													✓					
Δ end-tidal CO ₂ and $\dot{V}O_2$													✓					

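### The patient risk text in Protocol 8.5.2 presents safety as shown and leaves out exhaustion, while 8.3 and 8.4.1 are more guarded and report exhaustion as important

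*Protocol*

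**What the plan says.** Section 8.5 of the Protocol is headed as the lay summary of risks and benefits to be communicated to patients. Within it, 8.5.2 begins: "Previous studies have shown that aerobic exercise is safe for people to do in the first week after stroke". It then gives 276 bouts in the first week after stroke (237 walking, 32 seated cycling or stepping, 7 sit-to-stand). It lists cardiovascular, neurological and musculoskeletal complications (below 1%), lower-limb pain (below 2%), foot blisters or wounds (1.1%) and dizziness (below 7%). Exhaustion, tiredness and the lack of long-term data do not appear.

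Other sections read differently:

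- Section 8.3: "Low- to moderate-intensity aerobic exercise is considered to be safe for medically stable acute ischaemic stroke patients without contraindications". It adds that none of the studies it describes reported follow-up safety outcomes. It says exhaustion is not classed as an adverse event but matters for tolerability, and gives 24 of 224 treadmill sessions ended early for exhaustion, in 9 of 20 participants.
- Section 8.4.1 calls the intervention low risk, then says: "However, there is a lack of reported long-term follow-up outcomes". Because of that uncertainty it proposes that "this intervention should be categorised as type B, that is, somewhat higher than the risk of standard medical care".
- Section 4.3, on the same treadmill study, gives 28 sessions ended for exhaustion (participants not reported), 8 cancelled for tiredness, 4 ended for dizziness, and a 30-day follow-up without serious adverse events.

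**The concern.** The text meant for patients is firmer than the evidence summary and the risk rating it should reflect. The uncertainty that moves the intervention into type B is stated in 8.4.1 and missing from 8.5.2. The same lay summary does qualify the benefits: 8.5.1 says twice that an effect has only been shown in animals. Only the safety statement stands unqualified.

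The omission of exhaustion matters because, of the reasons for early stopping that the Protocol reports for the treadmill study, it is the most frequent, and because much rarer events such as blisters are listed. At stake is the accuracy of consent from patients who, under section 7.2, are asked to decide within 48 hours in the first week or so after a stroke. Design, analysis and progression criteria are not affected.

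**Working it through.** **Reproducing the lay figures.** 237 + 32 + 7 = 276. Dizziness is 19/276 = 6.9%, matching below 7%. Pooled adverse events are 33/276 = 12.0%, matching the mean in 8.3.

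**Rebuilding the 276 from 8.3.**

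- Walking: 224 treadmill sessions + 13 completed walk tests (14 participants, one unable to complete) = 237.
- Seated cycling or stepping: 28 graded tests + 4 sessions from the trial team's own preliminary study = 32.
- Sit-to-stand: 7.

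That the 28 graded tests are among the seated bouts is inferred from this exact match; the Protocol does not say so.

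**First-week claim.** The 28 graded-test participants were at a median of 9 days (range 5 to 11). With 28 ordered values and a median of 9, at least 14 lie at day 9 or later. So at most 276 − 14 = 262 bouts fell within days 1 to 7, and at most 32 − 14 = 18 of the seated ones. Section 8.3 itself says that the split between acute and subacute patients was not specified.

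**What zero serious events supports.** Exact 95% upper limits for no events:

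| Denominator | One-sided, 1 − 0.05^(1/n) | Two-sided, 1 − 0.025^(1/n) |
|---|---|---|
| 276 bouts, treated as independent | 1.08% | 1.33% |
| 73 participants (20 + 21 + 28 + 4) | 4.0% | 4.9% |

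Bouts cluster within people, so the bout-level limits are optimistic. The record fits a low risk but does not show safety, and it says nothing about longer-term effects.

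**Exhaustion against dizziness, treadmill study.**

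| | 8.3 count | 4.3 count |
|---|---|---|
| Sessions ended for exhaustion | 24/224 = 10.7% | 28/224 = 12.5% |
| Sessions ended for dizziness | not given | 4/224 = 1.8% |
| Exhaustion on the lay denominator | 24/276 = 8.7% | 28/276 = 10.1% |

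On stopped sessions the ratio is 24/4 = 6 to 28/4 = 7. On the lay denominator, either count exceeds the largest listed risk (dizziness, 6.9%). Per participant, 9/20 = 45% (exact 95% interval 23.1% to 68.5%), although 4.3 says this number was not reported.

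**Volume comparison.** Planned here: 10 + 15 + 20 + 25 + 30 = 100 minutes of conditioning, once daily, in bed. Treadmill study: 2 × 30 × 5 = up to 300 minutes, upright. The planned volume is about one third.

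**The case against.** **What stands.** Section 8.4.1 does say low risk, and its uncertainty concerns long-term outcomes, so 8.5.2 overstates the evidence without reversing it. Leaving out exhaustion follows the Protocol's own decision not to class it as an adverse event. Fatigue is taken seriously elsewhere: sections 12.3.3 and 14.2.1 describe shorter starting sessions, rest intervals and resistance adjusted to perceived exertion. Patients who enrol have also been screened as medically stable. That answers the qualification in 8.3 only in part, because sections 7.6 and 8.1 let the Study Doctor admit patients with relative contraindications.

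**Stronger readings that the documents do not support.**

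- A reader might infer that patients are never told about exhaustion. The participant information sheets and Figure 4 are not available, and 7.2 says that risks, benefits and burden are discussed. The omission is established only for the text of 8.5.2.
- A reader might infer that this programme adds the very exercise volume linked to adverse events. Section 8.3 says: "The higher frequency of AEs appears to be related to high exercise volume and the mode of exercise training". Its example is treadmill exercise twice daily for five days, about three times the volume planned here. This programme adds volume only relative to the single-bout studies, for which 8.3 reports no adverse events.
- A reader might apply the treadmill rates to this trial's intervention arm. They come from 20 patients walking upright at higher volume, and nothing in the Protocol says how they carry over to in-bed cycling.
- A reader might rely on 8.3 for a complete absence of follow-up. Section 4.3 reports 30 days without serious adverse events in the treadmill study. The two need reconciling, though 30 days does not close the long-term gap named in 8.4.1.

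**Conclusion.** The point holds as a correction to patient-facing risk wording. Section 8.5.2 states safety more firmly than 8.3 and 8.4.1 allow, and omits a tolerability outcome that ended 10.7% to 12.5% of sessions in the only training study, six to seven times as many as dizziness ended. Its first-week count is too high by at least 14 bouts, provided the graded tests are part of the 276, as the totals imply. Two internal conflicts sit beside it: 24 against 28 exhaustion stops (with 9 of 20 participants in one place and not reported in the other), and no follow-up against a 30-day follow-up.

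The conclusion does not need treadmill exhaustion rates to recur with in-bed cycling. It needs only that text listing risks for patients should agree with the Protocol's own evidence and rating.

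**What to change.** 1. Replace the first sentence of 8.5.2 with a statement that no serious adverse events were reported in a few small studies, that longer-term effects are not known, and that the intervention is rated somewhat higher risk than standard care.
2. Add tiredness or exhaustion to the list with its observed frequency per session and, once confirmed, per participant. Note that it comes from twice-daily treadmill walking at a higher volume than planned here.
3. Correct the claim that all 276 bouts took place in the first week, and the matching acute-phase total in 8.3.
4. Reconcile 24 (8.3) with 28 (4.3) exhaustion stops, including whether the number of participants was reported, and reconcile the follow-up statements in 8.3 and 4.3.
5. Check both participant information sheets and Figure 4 against the revised text.

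The cost is a few sentences, any approval needed for changed patient materials, and possibly slightly lower uptake.
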